11.3. Database Design

The eCRF is constructed in the EDC system by the CRO's Data Department, and the process should meet the requirements of the FDA 21 CFR Part 11. The database should manage the system login, data entry, modification, deletion and other data traces, and the establishment of

the database should adopt the standards of the Clinical Data Interchange Standards Consortium (CDISC).

The sponsor should have written procedures to ensure that their changes to eCRF are necessary, recorded, and approved by the investigator. The investigator should keep records of revisions and corrections.

11.4. Data Entry and Modification

The investigator or the site staff authorized by the investigator should fill in and modify the eCRF in accordance with the instructions provided by the CRO's Data Department. The CRA does not have this authority. The investigator should ensure that the data in various eCRF and other reports is accurate, complete, clear and timely. All data should be entered into the EDC during the visit or as soon as possible after the visit, and data entry should be carried out in strict accordance with the principle of "what you see is what you record". The EDC must be kept up-to-date to ensure that it reflects the latest dynamics of the subjects. If certain assessments are not carried out during the study, or certain information is unavailable, inapplicable or unknown, the investigator or the authorized site staff should record it in the eCRF.

The data in eCRF will be delivered to the data server. The investigator must review the data to ensure the accuracy and correctness of all entered data, and electronically sign the verified data. The signed information (including the date of signing) will be stored in the audit trail and shall not be changed.

The data in the eCRF should be consistent with the source file. If there is any inconsistency, a reasonable explanation should be made. Any correction or modification of eCRF made by the investigator or the authorized site staff should make the initial record clear and identifiable, keep the modification trails, explain the reason if necessary, and sign and date the modification. Change to the data that have been approved require the investigator to electronically sign again.

11.5. Data Verification

According to the finalized data verification plan, data manager will set up a data logic check program in the EDC system.

After the data is entered into the EDC system, the data will be verified through computer logic check and manual verification to ensure the logic, consistency and accuracy of the data.

After the data is entered into the EDC system, if there is any data that does not conform to logic, the system logic check will start operation and trigger a query. These queries need to be reviewed and answered by the investigator or personnel authorized by the investigator. When the updated data makes the logic check no longer valid, the data query will be immediately closed; when the study site confirms the data and provides a response, data manager needs to review and respond to the information. If the reason provided by the study site is reasonable, the data query will be closed; if the data problem is not resolved, data manager can continue to

communicate with the study site by continuing to add data queries until the data problem is finally resolved.

The subject data list/report is generated by programming to support manual data verification throughout the research process. When any data needs to be clarified/verified/confirmed by the investigator, manual queries can be added to the EDC system. These queries will be manually closed after the data is corrected or confirmed. The query will be recorded in the audit trail of the EDC system, including the operator's name, time and date.

The data manager should ensure that all queries are resolved before the database is locked, and the investigator should complete all electronic signatures in the EDC system to ensure the completeness and accuracy of the subject data in the EDC system.

11.6. Medical Coding

The data manager of the CRO's Data Department is responsible for the medical coding work of this study. The coding content includes medical history, AE, prior/concomitant medication, and prior/concomitant non-drug treatment.

Medical history and AEs will be coded according to the MedDRA (Version 22.1 or above) and submitted in the form of System Organ Class (SOC) and preferred terms. Prior medications and concomitant/concurrent medications will be coded using the World Health Organization Drug Dictionary (WHODD) (September 2018 version or above), and only the versions confirmed by the sponsor will be used for all dictionaries.

During the coding process, if there is a problem that any data cannot be coded due to improper, inaccurate, or vague medical terms, data manager will ask the investigator to verify and confirm by way of data queries.

Before the database is locked, data manager should send a medical coding report to the sponsor, which must be reviewed by the sponsor.

11.7. Data Locking

After reviewing and confirming that the established database is correct, the principal investigator, the sponsor, and the statistician will jointly decide to lock the database, and data manager will lock the database in the EDC system. In principle, the locked database is not allowed to be changed. If any data that needs to be modified is discovered after the data is locked, the main principal investigator, the sponsor, the statistician and data manager must agree to unlock the database before modifying it, and save written records and signatures of all parties.

12. Statistical Analysis

12.1. Statistical Analysis Plan

This section explains the statistical methods used for safety and efficacy analysis. The final analysis methods and specific details will be recorded in the official Statistical Analysis Plan

(SAP), where PK and PD analyses will be described separately in a PK/PD SAP. The SAP will be completed before the database is locked, and include detailed information on how to generate variables, how to handle missing data, and how to present the data, as well as detailed information on statistical methods used for safety and efficacy analysis. The final clinical study report will discuss deviations from the SAP (if any).

12.2. Statistical Hypothesis

Primary hypothesis:

H0: There is no efficacy difference between the CBP-201 300 mg Q2W group and the placebo group at W16 of treatment;

H1: There is an efficacy difference between the CBP-201 300 mg Q2W group and the placebo group at W16 of treatment.

12.3. Basis of Sample Size

The sample size of 255 cases (in a 2:1 ratio, 170 cases in the CBP-201 300 mg Q2W group, and 85 cases in the placebo group. Assuming that the dropout rate in the treatment group is 15%, then about 144 cases in the CBP-201 300 mg Q2W group and 72 cases in the placebo group will be able to complete the study) can provide a power of 90% to detect the therapeutic effect on the primary endpoint in the CBP-201 300 mg Q2W group and the placebo group. This power is calculated based on the following assumption: the proportion of subjects reaching the primary efficacy endpoint is 27% in the CBP-201 300 mg Q2W group and 9% in the placebo group, and the significance level for two-sided tests is 0.05.

Based on the results of another conducted phase II international multicenter clinical study of CBP-201 in patients with moderate-to-severe atopic dermatitis, the proportion of subjects reaching the primary efficacy endpoint was 28.1% in the CBP-201 300mg Q2W group and 10.7% in the placebo group, at a two-sided test significance level of 0.05, and if the results of this trial are similar to that of the WW001 trial, the above sample size would provide a power of more than 85% to detect the therapeutic effect on the primary endpoint between the CBP-201 300 mg Q2W group and the placebo group. Therefore, no adjustment is made to the sample size.

The primary analysis of this study will still be based on the 255 subjects enrolled in accordance with V2.1 and its earlier versions of the protocol. Subjects newly enrolled (approximately 81 cases) based on the protocol after V2.1 will not be included in the primary analysis, and only supplementary analysis will be performed.

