Statistical methods	
Determination of sample size
 
The sample size of 255 cases (in a 2:1 ratio, 170 cases in the CBP-201 300 mg Q2W group, and 85 cases in the placebo group. Assume that the dropout rate in the treatment group is 15%, then about 144 cases in the CBP-201 300 mg Q2W group and 72 cases in the placebo group will be able to complete the study) can provide a power of 90% to detect the therapeutic effect on the primary endpoint in the CBP-201 300 mg Q2W group and the placebo group. This power is

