	
calculated based on the following assumption: the proportion of subjects reaching the primary efficacy endpoint is 27% in the CBP-201 300 mg Q2W group and 9% in the placebo group, and the significance level for two-sided tests is 0.05.
 
The primary analysis of this study will still be based on the 255 subjects enrolled in accordance with V2.1 and its earlier versions of the protocol. Subjects newly enrolled (approximately 81 cases) based on the protocol after V2.1 will not be included in the primary analysis, and only supplementary analysis will be performed.
 
Statistical analysis populations
 
In this study, it is planned to perform statistical analyses in two stages:
 
First of all, after the 255 subjects enrolled based on the V2.1 and prior versions of the protocol complete the administration and treatment, related evaluations and follow-up of Stage 1 (W16 pre-dose visit), the primary analysis will be performed based on the data of the 255 subjects, and the following 6 analysis populations are defined as:
 
• Screening set 1 will include all subjects who have signed the ICF.• Randomization set 1 will include all subjects randomized at baseline (D1), regardless of whether they have received the treatment of study drug.• Full analysis set 1 (FAS1) will include all subjects in randomization set 1 who have received at least one dose of the study drug. FAS1 will determine the treatment groups based on the planned treatment.• Per protocol set 1 (PPS1) will include all subjects in FAS1 without any major protocol deviation.• Safety set 1 (SS1) will include all subjects who have received at least one dose of study drug. SS1 will determine the treatment groups based on the actually received treatment.• PK set 1 (PKS1) will include subjects in randomization set 1 who have received at least one dose of CBP-201 active drug and had at least 1 collected and analyzable PK sample. 
After all subjects (including approximately 81 additional subjects enrolled) entering Stage 2 have completed the treatment, evaluations and follow-up of Stage 2, a Stage 2 analysis will be performed.
 
The Stage 2 analysis is defined as the following 6 analysis populations:
 
• Randomization set 2 will include all subjects entering Stage 2, including all subjects who are randomized into Group C or Group D, and subjects entering Group E.• Full analysis set 2 (FAS2) will include all subjects in randomization set 2 who have received at least one dose of study drug in Stage 2. FAS2 will determine the treatment groups based on the planned treatment.• Per protocol set 2 (PPS2) will include all subjects in FAS2 without any major protocol deviation.• Safety set 2 (SS2) will include all subjects in randomization set 2 who have received the at least one dose of study drug in Stage 2. SS2 will determine the treatment groups based on the actually

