12.4. Analysis Populations

In this study, it is planned to perform statistical analyses in two stages:

First of all, after the 255 subjects enrolled based on the V2.1 and prior versions of the protocol complete the administration and treatment, related evaluations and follow-up of Stage 1 (W16

pre-dose visit), the primary analysis will be performed based on the data of the 255 subjects, and the following 6 analysis populations are defined as:

- Screening set 1 will include all subjects who have signed the ICF.
- Randomization set 1 will include all subjects randomized at baseline (D1), regardless of whether they have received the treatment of study drug.
- Full analysis set 1 (FAS1) will include all subjects in randomization set 1 who have received at least one dose of the study drug. FAS1 will determine the treatment groups based on the planned treatment.
- Per protocol set 1 (PPS1) will include all subjects in FAS1 without any major protocol deviation.
- Safety set 1 (SS1) will include all subjects who have received at least one dose of the study drug. SS1 will determine the treatment groups based on the actually received treatment.
- PK set 1 (PKS1) will include subjects in randomization set 1 who have received at least one dose of CBP-201 active drug and had at least 1 collected and analyzable PK sample.

After all subjects (including approximately 81 additional subjects enrolled) entering Stage 2 have completed the treatment, evaluations and follow-up of Stage 2, a Stage 2 analysis will be performed. The Stage 2 analysis will be defined as the following 6 analysis populations:

- Randomization set 2 will include all subjects entering Stage 2, including all subjects who are randomized into Group C or Group D, and subjects entering Group E.
- Full analysis set 2 (FAS2) will include all subjects in randomization set 2 who have received at least one dose of study drug in Stage 2. FAS2 will determine the treatment groups based on the planned treatment.
- Per protocol set 2 (PPS2) will include all subjects in FAS2 without any major protocol deviation.
- Safety set 2 (SS2) will include all subjects in randomization set 2 who have received at least one dose of study drug in Stage 2. SS2 will determine the treatment groups based on the actually received treatment.
- Safety set 3 (SS3) will include all subjects in SS1 and SS2 who have received at least one dose of the study drug.

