3.2. Sample Size

It is planned to enroll 255 subjects (in a 2:1 ratio, 170 subjects in the CBP-201 300 mg Q2W group, and 85 subjects in the placebo group) who will randomly receive either CBP-201 300 mg Q2W or placebo.

This sample size provides a power of approximately more than 90% to detect the difference between groups at a two-sided significance level of 5% under the assumption that 27% and 9% of subjects in the CBP-201 Q2W group and the placebo group can achieve an IGA score of 0-1 at W16 for the primary endpoint, respectively, accounting for a dropout rate of 15%.

Based on the results of another completed phase II international multicenter clinical study of CBP-201 in patients with moderate-to-severe atopic dermatitis, the proportion of subjects achieving the primary efficacy endpoint was 28.1% in the CBP-201 300 mg Q2W group and 10.7% in the placebo group, at a two-sided significance level of 0.05. If the results of this trial are similar to that of the WW001 trial, the above sample size would provide a power of more than 85% to detect the difference of the therapeutic effect on the primary endpoint between the CBP-201 300 mg Q2W group and the placebo group. Therefore, no adjustment is made to the sample size.

The primary analysis and Stage 2 analysis of this study will still be based on the 255 subjects enrolled in accordance with V2.1 and its earlier versions of the protocol. Subjects newly enrolled (a total of 75 cases) based on the protocol after V2.1 will not be included in the primary analysis and Stage 2 analysis, and only supplementary analysis will be performed.

4. Study Endpoints

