7.4. Efficacy Analysis

Efficacy analysis in Stage 1 will be performed based on FAS1 and PPS1, mainly the FAS1.

In order to control the type I error rate for multiplicity, a fixed-sequence method will be used. First of all, the active treatment group and the placebo group will be compared for the primary efficacy endpoint; when the primary efficacy endpoint reaches statistical significance, the active treatment group and the placebo group will be compared for the key secondary efficacy endpoints according to the sequence specified in the protocol.

Efficacy analysis in Stage 2 will be performed based on FAS2.

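### Is the stated 90% power unsound because it is computed on 144 v 72 completers while the primary analysis uses all dosed subjects (about 170 v 85)?

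*Protocol*

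**What the plan says.** Protocol 12.3 and the synopsis plan 255 subjects, 170 on CBP-201 300 mg Q2W and 85 on placebo. The dropout step reads "Assuming that the dropout rate in the treatment group is 15" per cent, which leaves "about 144 cases in the CBP-201 300 mg Q2W group and 72 cases in the placebo group will be able to complete the study". This sample "can provide a power of 90% to detect the therapeutic effect on the primary endpoint", on the assumption that "the proportion of subjects reaching the primary efficacy endpoint is 27% in the CBP-201 300 mg Q2W group and 9% in the placebo group", at two-sided 0.05. Protocol 12.3 then takes 28.1% v 10.7% from the other phase II trial, states a power above 85%, and leaves the sample size unadjusted.

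Section 3.2 of both SAP versions gives 170 and 85 without the completer counts: "This sample size provides a power of approximately more than 90% to detect the difference between groups", with 15% dropout allowed for. It describes the rates as applying to "27% and 9% of subjects in the CBP-201 Q2W group and the placebo group".

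On the analysis side, Protocol 12.4 states that "Full analysis set 1 (FAS1) will include all subjects in randomization set 1 who have received at least one dose of the study drug", and SAP 7.4 states "Efficacy analysis in Stage 1 will be performed based on FAS1 and PPS1, mainly the FAS1". Under Protocol 12.7.2 and 12.7.3 (Tables 12.1, 12.2 and 12.4), rescue for poor effect with a major impact and discontinuation for adverse events count as non-response. Values still missing after that are imputed, by multiple imputation in placebo and by jump-to-reference (J2R) in CBP-201.

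**The concern.** Taking dropouts off the sample size suits an analysis that excludes them, and this one keeps them. Dropout then acts on the response rates instead of the denominators. If 27% and 9% already describe whole arms, removing 15% counts dropout twice and understates power. If they describe completers, the whole-arm rates are lower and power may fall short of 90%.

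The text does not say which reading is meant. The 15% is also loosely worded: it names the treatment group, but the 72 shows that it was applied to placebo too, and its period is not given. Since Protocol 12.3 uses this calculation to justify keeping the sample size, a reader could suspect that the decision rests on the wrong sample.

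**Working it through.** **Inputs.** Protocol 12.3: two-sided 0.05; 170 v 85; 15% dropout; 27% v 9%; 28.1% v 10.7%. Completers: 170 × 0.85 = 144.5 and 85 × 0.85 = 72.25, the stated 144 and 72.

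**Formula.** Pooled-variance test of two proportions, unstratified:

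power = Φ( [ |p1 − p2| − 1.96 × s0 ] / s1 )

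where s0 = √[ p̄(1 − p̄)(1/n1 + 1/n2) ], s1 = √[ p1(1 − p1)/n1 + p2(1 − p2)/n2 ], and p̄ is the response rate over both arms.

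**Step 1: reproduce the plan's figures on 144 v 72.**

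- 27% v 9%: p̄ = 0.210, s0 = 0.0588, s1 = 0.0501; (0.180 − 0.1152)/0.0501 = 1.29; power 90.2%. Stated: 90%.
- 28.1% v 10.7%: p̄ = 0.223, s0 = 0.0601, s1 = 0.0523; (0.174 − 0.1178)/0.0523 = 1.08; power 85.9%. Stated: more than 85%.

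Both reproduce, so both are completer-sample figures.

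**Step 2: whole-arm rates on 170 v 85.**

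- 27% v 9%: s0 = 0.0541, s1 = 0.0461; (0.180 − 0.1061)/0.0461 = 1.61; power 94.6%.
- 28.1% v 10.7%: s0 = 0.0553, s1 = 0.0481; (0.174 − 0.1084)/0.0481 = 1.37; power 91.4%.

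**Step 3: completer rates on 170 v 85.** Let a fraction f of each arm be missing or failed at W16. There are two extremes:

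- All imputed: CBP-201 becomes p1(1 − f) + p2·f, and placebo stays at p2.
- All failed: both rates are multiplied by (1 − f).

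At f = 15%, 27% v 9% becomes 24.3% v 9.0% or 22.95% v 7.65%.

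| f, both arms | 27% v 9%: imputed / failed | 28.1% v 10.7%: imputed / failed |
|---|---|---|
| 10% | 90.0% / 91.3% | 85.5% / 87.1% |
| 15% | 86.8% / 89.1% | 81.6% / 84.5% |

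Power at 27% v 9% crosses 90% at f = 9.9% (imputed) or 13.0% (failed). These thresholds assume equal loss in both arms and this formula. With exact chi-square power they are 10.9% and 14.7%. With failures in the active arm only, the crossing is at 6.6%.

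**Step 4: which reading is likelier?** The other phase II trial had 226 subjects randomized 1:1:1:1 (Protocol 4.4.4), so 226/4 = 56.5, or 56 to 57 per arm. Among denominators from 40 to 59, 28.1% arises only as 16/57 and 10.7% only as 6/56. Both are full-arm denominators. SAP 3.2 also words the 27% and 9% as shares of the subjects in each group, and the endpoint definition counts failures as non-responders. The source of 27% and 9% is not given, so this is an inference.

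**The case for a change.** The strongest case for acting is that a stated power should belong to the planned analysis, and here a reader cannot tell whether it is about 95% or about 87%. At the protocol's own 15%, the completer reading puts both stated figures out of reach. Nor is 15% a ceiling: a subject who uses topical rescue for poor effect for more than 7 days counts as a failure but may complete the study, so the fraction missing or failed can exceed the dropout rate. At f = 20%, power at 27% v 9% is 82.9% (imputed) to 86.5% (failed). The correction would be a few words.

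The mismatch of samples and the undefined terms stand. The shortfall is not shown, because it needs both the less likely reading and a sizeable W16 loss. Dropout over the whole study would also overstate W16 dropout, although the 15% may already refer to Stage 1. SAP 3.2 never mentions 144 or 72, and its claim of more than 90% is true on the whole-arm reading. Inflating enrolment so that enough subjects remain after dropout is ordinary practice, and it errs on the safe side when the rates are whole-arm rates.

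**Conclusion.** No change is needed. The arithmetic is right on its stated inputs, and neither stated power is shown to be missed. On the whole-arm reading the plan understates its power by about 4 to 6 points (94.6% against 90.2%, and 91.4% against 85.9%). On the completer reading with 15% lost in both arms it would fall about 1 to 3 points short of 90% (86.8-89.1%), and about 0.5 to 3.4 points short of 85% at the other trial's rates (81.6-84.5%).

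The decision not to adjust the sample size is therefore not shown to be wrong. What is missing is a sentence saying whether the rates are whole-arm or completer rates and which period the 15% covers. Supplying it would alter no analysis set, test, significance level or enrolment figure.

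The figures assume an unstratified test and leave out the extra variance from imputation; the completer-reading figures also assume equal loss in the two arms. The preference for the whole-arm reading rests on wording and on rounding, not on a stated source.

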12.4. Analysis Populations

In this study, it is planned to perform statistical analyses in two stages:

First of all, after the 255 subjects enrolled based on the V2.1 and prior versions of the protocol complete the administration and treatment, related evaluations and follow-up of Stage 1 (W16

pre-dose visit), the primary analysis will be performed based on the data of the 255 subjects, and the following 6 analysis populations are defined as:

- Screening set 1 will include all subjects who have signed the ICF.
- Randomization set 1 will include all subjects randomized at baseline (D1), regardless of whether they have received the treatment of study drug.
- Full analysis set 1 (FAS1) will include all subjects in randomization set 1 who have received at least one dose of the study drug. FAS1 will determine the treatment groups based on the planned treatment.
- Per protocol set 1 (PPS1) will include all subjects in FAS1 without any major protocol deviation.
- Safety set 1 (SS1) will include all subjects who have received at least one dose of the study drug. SS1 will determine the treatment groups based on the actually received treatment.
- PK set 1 (PKS1) will include subjects in randomization set 1 who have received at least one dose of CBP-201 active drug and had at least 1 collected and analyzable PK sample.

After all subjects (including approximately 81 additional subjects enrolled) entering Stage 2 have completed the treatment, evaluations and follow-up of Stage 2, a Stage 2 analysis will be performed. The Stage 2 analysis will be defined as the following 6 analysis populations:

- Randomization set 2 will include all subjects entering Stage 2, including all subjects who are randomized into Group C or Group D, and subjects entering Group E.
- Full analysis set 2 (FAS2) will include all subjects in randomization set 2 who have received at least one dose of study drug in Stage 2. FAS2 will determine the treatment groups based on the planned treatment.
- Per protocol set 2 (PPS2) will include all subjects in FAS2 without any major protocol deviation.
- Safety set 2 (SS2) will include all subjects in randomization set 2 who have received at least one dose of study drug in Stage 2. SS2 will determine the treatment groups based on the actually received treatment.
- Safety set 3 (SS3) will include all subjects in SS1 and SS2 who have received at least one dose of the study drug.
- PK set 2 (PKS2) will include subjects who have received at least one dose of CBP-201 active drug in Stage 2 and had at least 1 collected and analyzable PK sample.

At stage 2, for subjects in group C or group D who have not achieved EASI-50 and are therefore assigned to group E to receive subcutaneous injection of CBP-201 300 mg every 2 weeks, their

efficacy variables and safety variables will be analyzed by assigned treatment groups or actual treatment groups and by stages.

The detailed definition of the statistical analysis data sets will be supplemented or adjusted in the SAP.

